12.3.3 Other Variables

Other variables include

Medical History

• Concomitant Medications/Treatments

12.4 Statistical Analysis Methods

12.4.1 General Considerations

All statistical analyses will be performed using SAS statistical analyses software (Version 9.2 or a newer version).

All safety analyses will use the SES. The primary effectiveness and secondary effectiveness analyses will be carried out on the PPS and for sensitivity of their analyses on the FAS. All other effectiveness (not primary and not secondary) analyses

Confidential and Proprietary Information. Do not disclose without authorization.

12.4.2 Effectiveness Endpoints

12.4.2.1 Primary Effectiveness Endpoint

The primary effectiveness endpoint is the difference in proportions of responding NLF sides (NLF sides with treatment success) in the Radiesse and Restylane groups at Month 6. The difference in proportions (D) is defined as the difference between the proportion of responders on the side treated with Radiesse (P_{test}) and the proportion of responders on the side treated with Restylane ($P_{control}$), i.e.:

$$D = P_{test} - P_{control}$$

As a result thereof, the null and the alternative hypothesis notations will be as follows:

$$H_0: D \le -\Delta$$
 (null) versus $H_1: D > -\Delta$ (alternative)

To test the non-inferiority of test in comparison to control, a two-sided 95% confidence interval (CI) will be constructed around D. The non-inferiority margin Δ , the clinically negligible difference, is 0.10 (or 10.0%). H₀ will be rejected if the lower bound of the 2sided 95% CI lies above the non-inferiority margin of $-\Delta$ (-10%), i.e. a conclusion of non-inferiority of Radiesse to Restylane.. The two-sided 95% CI for the differences between proportions (paired) will be constructed using the Newcombe's recommended method⁸ (Newcombe, 1998, method 10). The confirmatory analysis will be based on the PPS using observed values only.

12.4.2.2 Secondary Effectiveness Endpoint

The secondary effectiveness endpoint is the difference between the proportions (π_{test} - $\pi_{control}$) with an improvement at Month 6 in blinded evaluator's GAIS on the side treated with Radiesse (π_{test}) and on the side treated with Restylane ($\pi_{control}$).

The hypothesis on the secondary effectiveness endpoint and the corresponding analysis will be similar to that specified for the primary effectiveness analysis, however, using a less conservative margin of $\Delta = 0.15$ (or 15%). This analysis will be of exploratory nature without any inferential considerations.

Confidential and Proprietary Information. Do not disclose without authorization.

12.4.3 Safety Endpoints

The assessment of safety will be based mainly on the frequency of AEs and SAEs. Only treatment-emergent AEs will be summarized for each treatment group (as applicable) by the incidence of at least one event, the number of events, and the incidence using Medical Dictionary for Regulatory Activities (MedDRA) preferred terms within the system organ classes (SOCs).

Safety endpoints and/or variables with continuous outcomes will be analyzed using descriptive summary statistics including the number of non-missing observations, mean and standard deviation, median, upper and lower quartiles, minimum and maximum for values and changes from baseline. Categorical safety data (e.g. laboratory parameters with reference to normal ranges) will be analyzed using frequency tables and, if applicable, shift tables.

12.4.4 Other Endpoints

Other endpoints and/or variables will be analyzed strictly in an exploratory manner without any inferential considerations.

Baseline and demographic characteristics will be summarized by appropriate descriptive statistics (n, mean, standard deviation, median, range). Concomitant medications will be listed and summarized by Anatomical Therapeutic Chemical (ATC) class and World Health Organization Drug Dictionary (WHODD) preferred term.

12.4.5 Other Statistical/Analytical Issues

12.4.5.1 Significance Level and Power

Significance level and power was described in Section 12.1 Determination of sample size.

12.4.5.2 Expected Dropout Rate

Expected dropout rate was described in Section 12.1 Determination of sample size.

12.4.5.3 Planned Analyses and Early Termination of Study

Statistical analyses will be performed when all subjects reach the 6 Month post initial injection time point. Primary effectiveness variable, secondary effectiveness variables and AE data will be analyzed using the snapshot of data for the first 6 months. A Statistical and a Clinical Study Report will be generated for the aforementioned analysis. They will be amended by a description and discussion of the analyses performed when all subjects have completed the study. For further details on which tables are produced for the Clinical Study Report and which for the amendment, please refer to the SAP.

No examination for early termination is planned.

12.4.5.4 Discontinuations and Missing Data

Besides the analyses based on observed data, additional sensitivity analyses for primary and secondary effectiveness endpoints will be carried out with missing data imputed using single value imputation methods. Imputations will be performed until Month 6.

Missing effectiveness data and missing safety data will be imputed as follows:

Effectiveness:

Worst Case Scenario (WCS):

• For the WCS method, missing post-baseline data for Radiesse treatment group will be imputed as non-responders, while missing post-baseline data for Restylane treatment group will be imputed as responders. As a result, the WCS is considered a conservative imputation method because missing values from the control are imputed as responders while missing values from the treatment are imputed as non-responders. The WCS will be used for sensitivity analysis.

Further imputation methods will be described in the SAP.

Safety:

Each medication/therapy will be allocated unambiguously either to previous medications or to concomitant medications.

- If stop date is before start of treatment: Previous medication
- If the stop date is at or after start of treatment or ongoing is checked: Concomitant medication
- Otherwise, if the stop date is missing or partially given:
 - Partial stop date available: Previous therapy if the latest possible stop date is before start of treatment; Concomitant therapy if the latest possible stop date is at or after start of treatment
 - If the stop date is completely missing: Concomitant therapy

Each finding will be allocated unambiguously either to medical history or to concomitant diseases.

- If the stop date is before start of treatment: Medical history
- If the stop date is at or after start of treatment or ongoing (even if it refers to a cut-off point before start of treatment) is ticked: Concomitant disease
- Otherwise, if the stop date is missing or partially given:
 - Partial stop date available: Medical history if the latest possible stop date is before start of treatment; Concomitant disease if the latest possible stop date is at or after start of treatment
 - Stop date is completely missing for findings coded as "Surgical and medical procedures": Medical history
 - Stop date is completely missing for other findings: Concomitant disease

For AEs, imputation of missing start or stop dates will follow the steps below:

- If the start date (and time, if applicable) is partially missing but implies start before start of treatment or after date of final examination, the AE will be considered as Non- Treatment Emergent Adverse Event (TEAE).
 - If the start date (and time, if applicable) is partially missing and possibly after start of treatment and before or after date of final examination, will be considered as TEAE.

AEs with completely missing onset dates will be considered treatment emergent; no estimation of the dates will be performed.

13 DATA HANDLING AND RECORDKEEPING

Data required according to this protocol is to be recorded in the web-based eCRFs (electronic data capture system eClinicalOS). All users who will enter data into the eCRF will be previously trained in the Training Database. After the successful completion of the training all participants will complete the Training Record Form which will be a prerequisite for the access to the eCRF, and sent to Kuntuo Data Management related staff (or Kuntuo's CRA). By signing and dating the eCRF, the investigator will confirm that all investigations have been completed and conducted in compliance with the clinical study protocol, and that reliable and complete data have been entered into the eCRF.

All eCRF data collection will be performed through a secure web portal and all authorized personnel with access to the Electronic Data Capture (EDC) system must use personal credentials (username and password) to enter, review or correct data. Passwords and electronic signatures will be strictly confidential.

For the duration of the trial, the investigators will maintain complete and accurate documentation including but not limited to subject medical records, study progress records, laboratory reports, electronic case report forms, signed informed consent forms, device accountability records, and correspondence with the EC, monitor and Sponsor, adverse event reports, and information regarding subject discontinuation or completion of the study. Any source documentation (procedure reports, imaging studies, lab reports, death certificates, etc.) that is sent to the sponsor, reviewing committees, or the core lab, should have all subject identifiers removed and replaced with the subject number.

All data required by this clinical study protocol are to be entered into a validated database.

If corrections in the subject diary or subject scales are necessary, the subject should be instructed to make a correction by drawing only a single line through the error, leaving the incorrect entry legible. The subject should date and initial the correction. The investigator should not make any changes to these documents.

Essential documents at the investigational site include but are not limited to:

- (1) Subject files
- (2) Subject identification code list
- (3) A copy of the study protocol and any amendments
- (4) Investigator's copies of the CD/DVD, data clarification forms, and any associated subject-related source data
- (5) Signed informed consent forms
- (6) Copies of all direct correspondence with the EC, with the regulatory authority(ies), and with the sponsor

- (7) Copies of laboratory normal ranges and methods
- (8) Copies of investigational product disposition records

Essential documents should be retained per applicable regulations and as instructed by the study sponsor. Study documents may not be destroyed by study site personnel prior to the required retention period. The investigator/institution must inform the sponsor in due time if the PI leaves the institution during the retention period. This rule also applies when the institution closes within the retention period.

14 **PROTOCOL DEVIATIONS AND AMENDMENTS**

14.1 **Protocol Deviation**

Investigators will adhere to the protocol which has been agreed between Principal Investigators and the Sponsor and approved in writing by the EC consulted by the head of the investigational site.

Investigators will not deviate from or alter the protocol without written agreement between the Principal Investigator (PI) and the Sponsor and written approval by the EC based on prior review. Exceptionally, in case of urgent clinical need such as to minimize emergent risk to a subject, Investigators may deviate from the protocol without written agreement between the PI and the Sponsor and written approval by the EC based on prior review.

Investigators must document all deviations from the protocol using the Protocol Deviation (PD) Form from the subject-specific eCRF for whatever reason.

Only in case a deviation occurred due to urgent clinical need such as to minimize emergent risk to a subject, the Investigator will document the rationale for the deviation for immediate submission to the head of his/her investigational site and retain a copy and document the deviations from the protocol using the PD Form from the subject-specific eCRF. If the Investigator proposes that the protocol be amended, the Investigator may recommend changes to the sponsor. The sponsor will determine if it is appropriate to amend the protocol at which time the protocol will be reviewed by all site ECs for approval and use throughout the study.

In the event that an Investigator does not comply with Clinical Study Agreement or protocol, the Sponsor will be notified of the site's non-compliance.

In the event of repeated non-compliance, as determined by the Sponsor, a Sponsor's monitor or company representative will attempt to secure compliance by one or more of the following (and not limited to):

- Visiting the investigator
- Telephoning the investigator
- Corresponding with the investigator

Repeated non-compliance with the signed agreement, the protocol or any other conditions of the study may result in further escalation in accordance with the Sponsor's written procedures including securing compliance or, at its sole discretion; Sponsor may terminate the investigator's participation in the study.

Confidential and Proprietary Information. Do not disclose without authorization.

14.2 **Protocol Amendments**

Approved protocol amendments will be provided to the Investigators by the Sponsor prior to implementing the amendment. The Principal Investigator is responsible for notifying the EC of the protocol amendment (administrative changes) or obtaining EC's approval of the protocol amendment (changes in subject care or safety), according to the instructions provided by the Sponsor with the protocol amendment.

Acknowledgement/approval by the EC of the protocol amendment must be documented in writing prior to implementation of the protocol amendment. Copies of this documentation must also be provided to the Sponsor.

15 DIRECT ACCESS TO SOURCE DATA/DOCUMENTS

The Investigator/institution will permit direct access to source data/documents for studyrelated monitoring, audits, EC review, and regulatory inspections.

Subjects providing informed consent agree to allow Sponsor or designee access and copying rights to pertinent information in their medical records concerning their participation in this study. The Investigator will obtain, as part of the informed consent, permission for study monitors or regulatory authorities to review, in confidence, any records identifying the subjects in this study. This information may be shared with regulatory agencies; however, the Sponsor undertakes not to otherwise release the subject's personal and private information.

16 FINANCE AND INSURANCE

Merz will provide insurance in accordance with local guidelines and requirements as a minimum for the patients participating in this study. The terms of the insurance will be kept in the study files.
17 CLINICAL STUDY REPORT

A Clinical Study Report containing effectiveness and safety analyses will be generated after all subjects have completed the Month 6 visit. It will be amended by a description and discussion of the analyses performed when all subjects have completed the study. The content of the clinical study report and its amendment will meet the requirements of the Center of Medical Device Evaluation (CMDE).

19 PUBLICATION POLICY

The institution and investigators participating in this trial shall have no right to publish or present the results of this study without the prior written consent of Merz North America, Inc.

1 LIST OF ABBREVIATIONS

ADE	Adverse Device Effect
AE	Adverse Event
ATC	Anatomical Therapeutic Chemical
BDRM	Blind Data Review Meeting
BMI	Body Mass Index
CI	Confidence Interval
CSR	Clinical Study Report
eCRF	electronic Case Report Form
FAS	Full Analysis Set
GAIS	Global Aesthetic Improvement Scale
MedDRA	Medical Dictionary for Regulatory Activities
NLFs	Nasolabial Folds
PPS	Per Protocol Set
RS	Randomized Set
SADE	Serious Adverse Device Effect
SAE	Serious Adverse Event
SAP	Statistical Analysis Plans
SES	Safety Evaluation Set
TEAE	Treatment Emergent Adverse Event
WHODD	World Health Organization Drug Dictionary
WSRS	Wrinkle Severity Rating Scale

2 GENERAL AND TECHNICAL ASPECTS

The objective of this statistical analysis plan is to specify the statistical analyses in more detail than stated in the clinical study protocol and to be precise enough to serve as a guideline for statistical programming and creation of tables, figures and listings.

This statistical analysis plan is based on the clinical study protocol version 1.2, dated Oct 16th, 2017.

All programs will be written using SAS version 9.4. It will be assured that all programs run with SAS version 9.2, too, without errors or warnings. A preferred font size of 10 points, minimum font size of 8 points with a unique font size for the whole document required will be used for the tables and figures in section 14, corresponding to a linesize of 111 (8 points: 140) digits and a pagesize of 42 (8 points: 52) lines for an output in A4 landscape format. For listings, a standard font size of 10 points with the linesize and pagesize as defined above will be used to produce the output in A4 format. Single SAS programs will be written for all tables and figures, and all listings, respectively. All outputs will be transferred into PDF-files using the Merz internal SAS macro LST2PDF. These PDF-files will be generated separately for the tables and figures of section 14 and the listings of section 16.2 of the appendix of the clinical study report (CSR). Each PDF-file will include the corresponding table of contents, preceding the content of the file.

The standard TFLs v.6.0 will be applied.

3 CLINICAL STUDY DESIGN AND OBJECTIVES

3.1 Clinical Study Design

[figure not shown]
This is a 12-month, multicenter, non-inferiority, split-face, active comparator, randomized, blinded (evaluator and subject) study evaluating the effectiveness and safety of Radiesse versus Restylane for the correction of nasolabial folds (NLFs) in adult subjects.

Approximately 174 Chinese subjects will be enrolled into this study. Subjects will be enrolled at approximately 4 investigational sites in China.

During the baseline visit for each subject, one NLF will be randomized to be treated with Radiesse and the other with Restylane. Subjects will have the option of a touch-up injection in one or both NLFs 4 weeks after the initial injection with the same randomized treatment.

The end of the study is the date of the last visit of the last subject.

Figure 1: Study Flow Chart

3.2 Clinical Study Objectives

The objectives of this study are to evaluate the effectiveness and safety of Radiesse for the correction of NLFs.

4 DETERMINATION OF SAMPLE SIZE

The estimate of the sample size is based on the following assumptions:

- Estimate of treatment effects (i.e. proportion of responders) on Test (Radiesse) and Control (Restylane) sides are at least equal, i.e. $P_{test} \geq P_{control}$ (or $D = P_{test} - P_{control} \geq 0$).
- Non-inferiority margin, $\Delta = 10\%$ (i.e., maximum negligible difference between the test and control proportions).
- Type I error, $\alpha = 0.025$.
- Type II error $\beta = 0.2$ (i.e. statistical power, $1-\beta = 0.8$ or 80%).
- Proportion of pairs with discordant responses $\eta = 0.175$ (i.e. 17.5%).

Using the above assumptions for sample size calculation in nQuery yields 138 effectiveness evaluable subjects needed to carry out the non-inferiority hypothesis associated with the primary effectiveness endpoint. Accounting for a 20% attrition (attributable to dropout of subject and major protocol deviations), overall 20% more subjects will be enrolled resulting in a total of approximately 174 subjects that will be randomized into this trial.

Since this is a multi-center, competitive enrollment study, the target number of subjects to be enrolled per investigational site is 44. In order to ensure that adequate subjects are enrolled per investigational site for determination of treatment effect homogeneity (or lack thereof), a minimum of approximately 22 and maximum of approximately 66 subjects will be enrolled.

per investigational site. The specified proposed minimum and maximum number of subjects to be enrolled per investigational site minimizes the probability of any one site having a preponderance of treatment effect.

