12 STATISTICAL METHODS

This section describes the statistical analyses foreseen at the time of study planning. Further details on the statistical and analytical aspects will be presented in the SAP.

Any deviations from planned analyses, the reasons for such deviation, and all alternative or additional statistical analyses that may be performed before database close or unblinding, respectively, will be described in amendments to the clinical study protocol or the SAP. All deviations and/or alterations will be summarized in the clinical study report.

12.1 **Determination of Sample Size**

The estimate of the sample size is based on the following assumptions:

- Estimate of treatment effects (i.e. proportion of responders) on Test (Radiesse) and Control (Restylane) sides are at least equal, i.e. $P_{test} \ge P_{control}$ (or $D = P_{test} P_{control} \ge 0$).
- Non-inferiority margin, $\Delta = 10\%$ (i.e., maximum negligible difference between the test and control proportions).
- Type I error, $\alpha = 0.025$.
- Type II error $\beta = 0.2$ (i.e. statistical power, $1-\beta = 0.8$ or 80%).
- Proportion of pairs with discordant responses $\eta = 0.175$ (i.e. 17.5%).

Using the above assumptions for sample size calculation in nQuery yields 138 effectiveness evaluable subjects needed to carry out the non-inferiority hypothesis associated with the primary effectiveness endpoint. Accounting for a 20% attrition (attributable to dropout of subject and major protocol deviations), overall 20% more subjects will be enrolled resulting in a total of approximately 174 subjects that will be randomized into this trial.

This is a multi-center, competitive enrollment study. The target number of subjects to be enrolled per investigational site is 44. In order to ensure that adequate subjects are enrolled per investigational site for determination of treatment effect homogeneity (or lack thereof), a minimum of approximately 22 and maximum of approximately 66 subjects will be enrolled per investigational site. The specified proposed minimum and maximum number of subjects to be enrolled per investigational site minimizes the probability of any one site having a preponderance of treatment effect.

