7.1 Effectiveness Endpoints

For categorical variables, frequencies of raw values and (where applicable) frequencies of changes from baseline will be shown by treatment and visit together with means and standard deviations.

Response variables are shown by visit as number and percentage of subjects with response (=proportion) at that visit per treatment together with the difference of the (paired) treatment response proportions and its corresponding 95% confidence interval computed according to Newcombe's recommended method¹ [Newcombe, 1998, method 10]. In addition, cross tables are provided showing number (and percent) of subjects with response/non-response on the Radiesse treated side vs. response/non-response on the Restylane treated side by visit.

For WSRS raw values and changes from baseline as well as for blinded evaluator's GAIS, cross tables are prepared showing frequencies of values observed on the Radiesse treated side vs. values observed on the Restylane treated side by visit.

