Statistical analyses will be performed when all subjects reach the 6 Month post initial injection time point. Primary effectiveness variable, secondary effectiveness variables and AE data will be analyzed using the snapshot of data for the first 6 months. A Statistical and a Clinical Study Report will be generated for the aforementioned analysis. They will be amended by a description and discussion of the analyses performed when all subjects have completed the study. For further details on which tables are produced for the Clinical Study Report and which for the amendment, please refer to the TFLs.

No examination for early termination is planned.

7.4.3 *Data Monitoring Committee*

There will be no data monitoring committee for this study.

7.4.4 *Multiple Comparisons/Multiplicity*

Only the analysis of the primary effectiveness endpoint based on PPS using observed values is of confirmatory nature. Further analyses on the primary effectiveness endpoint are performed for sensitivity reasons. Analyses of all other endpoints/variables is of exploratory nature.

7.4.5 *Examination of Subgroups*

No subgroup examination will be performed for this study.

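### Do the site enrolment limits, justified partly by checking that the treatment effect is homogeneous across sites, require a by-site analysis that the plan does not show?

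*SAP*

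**What the plan says.** SAP 4 and Protocol 12.1 set a target of 44 subjects per site, with a minimum of about 22 and a maximum of about 66, at about 4 sites. Both documents give two reasons for the limits.

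- The first is homogeneity. The SAP sentence begins "In order to ensure that adequate subjects are enrolled per investigational site for determination of treatment effect homogeneity (or lack thereof", and the protocol has the same reasoning: "for determination of treatment effect homogeneity (or lack thereof), a minimum of approximately 22 and maximum of approximately 66 subjects".
- The second is balance between sites: the limits are said to be a choice that "minimizes the probability of any one site having a preponderance of treatment effect".

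The readable effectiveness analyses do not use site. SAP 7.1 says "Response variables are shown by visit as number and percentage of subjects with response (=proportion) at that visit per treatment", with the paired difference D and its 95% Newcombe interval, and then "In addition, cross tables are provided showing number (and percent) of subjects with response/non-response on the Radiesse treated side" against the Restylane side, by visit. SAP 7.1.1 defines one pooled D and one interval. The sensitivity analyses are a repeat on the Full Analysis Set and two imputation scenarios (SAP 7 and 7.4.1). SAP 7.4.5 reads "No subgroup examination will be performed for this study".

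**The concern.** Determining whether an effect is homogeneous across sites means looking at it by site. A programmer who follows only the readable SAP would produce no such table, and the subgroup sentence carries no exception for site. So a purpose written into both documents appears to have nothing that delivers it.

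The worry has some substance in a paired non-inferiority trial. One site may supply up to 66/174 = 37.9% of subjects. The interval for D is driven by discordant pairs. A site where nearly every subject gets the same result on both folds, for whatever reason, pulls the pooled D toward 0 and narrows the interval, and both movements favour non-inferiority. If that happened at a large site, a reader with only pooled counts could not say which site was responsible.

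**Working it through.** **1. The plan's own figures.** Inputs from SAP 4: one-sided alpha 0.025, power 80%, margin 0.10, discordant proportion 0.175, true D = 0.

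- n = (1.960 + 0.842)² × 0.175 / 0.10² = 137.4, rounded up to 138. This matches the plan.
- 138 / 0.80 = 172.5, or 173, consistent with about 174 randomized.
- 174 / 4 = 43.5, or 44 per site.

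None of these steps uses the site limits, so the sample size does not rest on the homogeneity clause.

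**2. What a by-site display could show.** Assume 80% of each site's subjects are evaluable, the planned 17.5% discordance holds at every site, and D = 0. Normal half-width = 1.96 × √(0.175/n). The Newcombe method 10 column also assumes response rates of 70 to 80%.

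| Enrolled | Evaluable n | Expected discordant pairs (0.175n) | Half-width, normal | Half-width, Newcombe | P(no discordant pair) = 0.825ⁿ |
|---|---|---|---|---|---|
| 22 | 18 | 3.2 | 19.3 points | 21.3–22.7 | 3.1% |
| 44 | 35 | 6.1 | 13.9 points | 14.7–15.4 | 0.12% |
| 66 | 53 | 9.3 | 11.3 points | 11.8–12.1 | 0.004% |

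Even the largest permitted site has a half-width above the 10-point margin. The display could expose a gross difference, or a larger site with no discordant pairs at all. It could not establish homogeneity.

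**3. What a formal test could show.** Take a chi-square heterogeneity test across four sites (3 degrees of freedom, 5% level, variance of each site's D equal to 0.175/n, 138 evaluable in total), with one site worse than the others. The noncentrality is Σ (nᵢ/0.175)(Dᵢ − D̄)², where D̄ is the size-weighted mean. For four sites of 34.5 and one at −10 points, D̄ = −2.5 points, so it is (34.5/0.175) × (0.075² + 3 × 0.025²) = 1.48.

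| One site worse by | Power, four sites of 34.5 | Power, deviating site has 17.6 (others 34.5, 34.5, 51.4) |
|---|---|---|
| 10 points | 15% | 11% |
| 20 points | 51% | 32% |
| 30 points | 88% | 65% |

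A non-significant result would say little about differences the size of the margin.

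**4. The two stated purposes against the text.** Limiting the weight of one site is achieved by the cap, with no analysis needed. The homogeneity clause sits in the sample-size section as a reason for how many subjects each site enrols. Homogeneity across sites is not among the objectives (SAP 3.2), and no analysis section promises it.

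**5. What cannot be seen.** SAP 7.1.3, directly after the secondary endpoint, is redacted, as is part of SAP 8 on the effectiveness analyses. Appendix 1, the list of tables, shows only its heading. SAP 7.4.2 refers to mock shells that specify each table, and they are not supplied. These are the places where a by-site table would be listed, so its absence is not established. SAP 7.4.5 does not name site, and many plans treat site as a conduct factor separate from patient subgroups.

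**The case for a change.** The best argument for acting is that it is cheap and that the mechanism is real. SAP 7.1 already plans the cross table and D with its interval by visit, so site would be one more grouping, and specifying it before unblinding avoids an unplanned table later.

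A case can be built in which it matters. Suppose (assumed counts) 53 subjects at one site all succeed on both sides, and the other 85 split 59/5/10/11 (both succeed, Radiesse only, Restylane only, neither). The pooled Newcombe lower limit is −9.6 points, which passes. If all 138 had followed the pattern of the 85, it would be −13.1, which fails.

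That case should carry little weight. If the large site shared the 59/85 rate of success on both sides seen elsewhere, 53 out of 53 would have probability (59/85)⁵³, about 4 in a billion, so it depicts a grossly aberrant site. The planned pooled cross table would also give a warning: 15/138 = 10.9% discordant against 17.5% assumed, and 15 or fewer has probability about 2% at 17.5%. What stands is that the pooled table cannot say which site is responsible.

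It also stands that, in the readable text, the homogeneity rationale is not followed up. But the added table would carry no decision rule and could not do what the clause describes. Deleting the clause would remove the mismatch, at the price of a protocol amendment with ethics committee notification or approval (Protocol 14.2), for a sentence that governs no analysis.

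**Conclusion.** The mismatch between the rationale and the readable analyses is genuine but minor, and no change is needed. Following the plan as written leaves the confirmatory comparison, the 138 evaluable subjects and the type I error as they are. A by-site table would be descriptive, with half-widths of about 11 to 23 points against a 10-point margin, and would leave homogeneity undetermined. If a question about a particular site arises, analysts can split the planned counts by site as a descriptive look, and Protocol 12 allows additional analyses to be described in an amendment to the protocol or SAP before database close or unblinding. A sponsor revising the documents for other reasons could add the display with an exception in SAP 7.4.5, point to an existing shell, or drop the clause. That is a matter of tidiness.

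The figures assume 80% evaluability and 17.5% discordance at every site, D = 0 for the half-widths, and response rates of 70 to 80% for the Newcombe values. The conclusion does not depend on whether a by-site table exists in the redacted text or the shells. If one does, even the mismatch largely disappears.
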